For the analysis of biomarker data, the actual treatment received will be used rather than the treatment assignment at enrollment. Descriptive statistics will be provided for all scheduled post-baseline times of measurement in Study M15-563, with all subjects who were administered a dose in Study M15-563 included. The descriptive statistics will also be provided for the baseline measurement. For subjects whose treatment in Study M15-562 was one of the ABBV-8E12 doses, the baseline value for Study M15-563 will be the baseline value of Study M15-562. For subjects whose treatment in Study M15-562 was placebo, the baseline value will be the last measurement obtained before the first dose of Study M15-563, which might be the last measurement of Study M15-562 as explained in Section 4.2.

Longer-Term Biomarker Data Set: Only data of subjects whose treatment in Study M15-562 was with one of the ABBV-8E12 dose levels will be included in this data set. The data set will include the data for all scheduled times of measurement of Study M15-563. The baseline value for this data set will be the baseline value of Study M15-562.

6.0 Demographics, Baseline Characteristics, Medical History, and Previous/Concomitant Medications

The data analysis will be conducted among treatment groups defined as Studies M15-562/M15-563: 2000/2000 mg, 4000/4000 mg, placebo/2000 mg, and placebo/4000 mg.

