10.0 Safety Analysis

10.1 General Considerations

Comparisons between treatment groups (Studies M15-562/M15-563) of interest will not be performed.

All other safety assessments that are taken no more than 45 days after the last dose of study drug will be included in the safety evaluation of the Treatment Period, and all safety assessments that are taken more than 45 days but not more than 20 weeks after the last dose of study drug will be included in the safety evaluation for the Post-treatment Follow-up Visit.

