12.2 Analysis on Treatment by ABBV-8E12 for at Least One Year

The data set on which this analysis will be performed is the Longer-Term Biomarker Data Set described in Section 5.1. All the measurements in this data set were obtained after a subject was on treatment with ABBV-8E12 for 52 weeks or longer.

Transformation of Variables for Analysis

If the probability distribution for a variable appears to have considerable non-symmetry (e.g., skewness coefficient > 1.00 in magnitude), a transformation will be sought that has an approximately normal distribution. If a transformation is employed, estimates of central values on the original scale (back transformation of SAS least squares means) will be provided. If the logarithmic transformation is used, the comparison of the treatments will be in terms of the ratio of central values.

Analysis of CSF and Plasma Concentration Variables

For CSF and plasma concentrations of tau, an MMRM analysis will be performed to compare the effects of the 2000 and 4000 mg doses of ABBV-8E12. The model will include classification by ABBV-8E12 dose and time of measurement. There will be an effect for the interaction of ABBV-8E12 dose and time of measurement. The subjects in each treatment group will be viewed as a random sample. The baseline value will be a covariate. The model will also initially have a term for the interaction of baseline value and visit.

After the structure of the covariance matrix is decided upon, as discussed below, a test will be performed on the term for the interaction of baseline value and visit. The term for this interaction will be removed from the model if the statistic is not significant at level 0.100.

Within the framework of the final model, the mean across the scheduled times of measurement will be estimated for each ABBV-8E12 dose level. The hypothesis of no difference between the main effects of the two ABBV-8E12 dose levels (i.e., a composite

assessment for the several times of times of evaluation) will be tested at significance level 0.050. The SAS least squares means (LS means) for the two ABBV-8E12 dose levels across time will be provided and presented graphically.

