13.0 Table and Appendix

Table 2. Study Activities

	Treatment Period ^a																	20 Wks Post Last Dose F/U																		
	Year 1																																			
	Dose 1	Dose 2	Dose 3	Dose 4	Dose 5	Dose 6	Dose 7	Dose 8	Dose 9	Dose 10	Dose 11	Dose 12	Dose 13	Dose 14	Dose 15	D/C																				
Visits & Procedures ^b	Day 1	Day 15	Day 29	Day 57	Day 85	Day 113	Day 141	Day 169	Day 197	Day 225	Day 253	Day 281	Day 309	Day 337	Day 365	Wk 2	Wk 4	Wk 8	Wk 12	Wk 16	Wk 20	Wk 24	Wk 28	Wk 32	Wk 36	Wk 40	Wk 44	Wk 48	Wk 52							
Subject/study partner ICF ^c	X																																			
Medical history update ^d	X																																			
Randomization	X																																			
Physical examination	X																																			
Symptom-driven physical examination ^e								X																										X		
Orthostatic vital signs ^{f,g}	X	X	X	X	X	X	X	X	X	X	X	X	X	X	X	X	X	X	X	X	X	X	X	X	X	X	X	X	X	X	X	X	X			
Vital signs ^g																																		X		
Body weight (prior to infusion)	X	X	X	X	X	X	X	X	X	X	X	X	X	X	X	X	X	X	X	X	X	X	X	X	X	X	X	X	X	X	X	X	X	X		
Pregnancy test (WOCBP) ^h	U				U			U																										U	S	U
Neurological examination	X				X			X																										X	X	
12-lead ECG	X				X			X																										X	X	
Clinical laboratory tests	X				X			X																										X	X	
Brain MRI ⁱ	X				X			X																										X	X	
LP/CSF collection ^j	X							X																										X	X	

Table 2. Study Activities (Continued)

		Treatment Period ^a																20 Wks Post Last Dose F/U																
		Year 1																																
		Dose 1	Dose 2	Dose 3	Dose 4	Dose 5	Dose 6	Dose 7	Dose 8	Dose 9	Dose 10	Dose 11	Dose 12	Dose 13	Dose 14	Dose 15	D/C																	
Visits & Procedures ^b	Day 1	Day 15	Day 29	Day 57	Day 85	Day 113	Day 141	Day 169	Day 197	Day 225	Day 253	Day 281	Day 309	Day 337	Day 365	Wk 2	Wk 4	Wk 8	Wk 12	Wk 16	Wk 20	Wk 24	Wk 28	Wk 32	Wk 36	Wk 40	Wk 44	Wk 48	Wk 52					
Blood PK sample	X				X			X																						X	X			
ADA Sample collection	X				X			X																						X	X			
Plasma biomarkers	X				X			X																					X	X	X			
CSF biomarkers	X							X																					X	X	X			
Optional exploratory PGx DNA and RNA blood sample	X				X																								X	X				
Administer IV Study Drug	X	X	X	X	X	X	X	X	X	X	X	X	X	X	X	X	X	X	X	X	X	X	X	X	X	X	X	X	X	X	X			
PSPRS	1				1																										1	1		
CGI-S	2				2																											2	2	

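### The longer-term biomarker data set has no post-dose cut-off, so read literally it brings plasma and CSF samples taken 20 weeks after the last dose into the tested 2000 versus 4000 mg comparison

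*SAP*

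**What the plan says.** - **Subjects and visits.** SAP 5.1 restricts the data set by earlier treatment: "Only data of subjects whose treatment in Study M15-562 was with one of the ABBV-8E12 dose levels will be included in this data set". It then takes every visit: "The data set will include the data for all scheduled times of measurement of Study M15-563". Time since the last dose is not limited.
- **What is estimated and tested.** Under SAP 12.2, "the mean across the scheduled times of measurement will be estimated for each ABBV-8E12 dose level". The test that follows concerns "The hypothesis of no difference between the main effects of the two ABBV-8E12 dose levels", taken as a composite over the times, at level 0.050. Sidedness is not stated.
- **The follow-up visit.** SAP 4.2 and Protocol 5.1 bring subjects back about 20 weeks after their last dose. Protocol Appendix C and SAP Table 2 give that visit its own column, and the plasma and CSF biomarker rows carry marks for it.
- **Cut-offs elsewhere.** Protocol 8.1.1 admits efficacy assessments up to 45 days after the last dose. SAP 10.1 moves safety assessments "taken more than 45 days but not more than 20 weeks after the last dose" into a separate follow-up evaluation. SAP 10.3.1 and 10.5.1 also keep post-treatment values apart. The biomarker sections contain no such rule.

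**The concern.** The analysis compares the two doses in subjects with at least a year of exposure, yet one of its time levels is measured when little drug is left. The main effect averages over time levels, so that level counts as much as any visit during dosing. If the doses separate on drug and converge off drug, the tested difference is pulled toward zero.

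The visit also fits the time factor badly because it is tied to the last dose. A subject whose last dose is at Week 52 has the follow-up near Week 72 (52 + 20). A subject dosed to Week 256 has it near Week 276 (256 + 20). The model would treat both as one time.

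This matters because SAP 9.0 drops the efficacy analyses and SAP 10.1 drops between-group safety comparisons. The SAP 12.2 tests, for tau and for the imaging variables, are the dose comparisons for which the SAP still sets out a test and a level.

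**Working it through.** The plan gives no effect size, variance or power for this analysis, so there is no design figure to reproduce.

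**1. Is a follow-up biomarker sample scheduled?** The tables are partly broken, so this rests on column position. In Protocol Appendix C, Year 1, the plasma and CSF biomarker marks after Week 52 fall in the same column as the follow-up urine pregnancy test, not the serum test at discontinuation. In Year 3 both rows are again marked in the follow-up column. In both years the serum PK row has the same end marks as the plasma biomarker row, and Protocol 5.3.2.1.1 names the follow-up PK sample in words. In SAP Table 2, Year 1, the "Plasma biomarkers" row and the CSF row each carry three end marks, which fits Week 52, discontinuation and follow-up. For MRI, SAP Table 2 Year 1 is unclear, although Protocol Year 1 shows a follow-up mark.

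**2. Does any sentence remove it?** SAP 12.2 states: "All the measurements in this data set were obtained after a subject was on treatment with ABBV-8E12 for 52 weeks or longer". Everyone in this data set had already received 52 weeks of ABBV-8E12, so a follow-up sample also satisfies that sentence.

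**3. How much drug is left?** Protocol 3.0 gives a half-life of 27 to 37 days. Twenty weeks is 140 days.
- Half-lives elapsed: 140/27 = 5.2 and 140/37 = 3.8. Protocol 6.1.4 says about 5.
- Remaining, counted from the last infusion: 0.5^(140/27) = 2.7% and 0.5^(140/37) = 7.3%.
- Plasma biomarker samples are drawn before infusion (Protocol 5.3.1.2.1), so a fairer reference is the trough 28 days after a dose. With 140 − 28 = 112 days, 0.5^(112/27) = 5.6% and 0.5^(112/37) = 12.3%, assuming mono-exponential decline.

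**4. How much does the contrast shrink?** Take K visits during the treatment period with equal dose difference, one follow-up visit that keeps a fraction f of it, and equal weights, as in default least squares means. The ratio of the tested contrast to the treatment-period contrast is (K + f)/(K + 1). The scale is that of the analysis, so it is the log ratio if a log transform is used.

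| Variable and times used | K | Loss if f = 0 | Loss if f = 0.5 |
|---|---|---|---|
| CSF, with optional Weeks 76, 128, 180, 232 | 11 | 1/12 = 8.3% | 4.2% |
| CSF, mandatory: Day 1, Weeks 24, 52, 104, 156, 208, 260 | 7 | 1/8 = 12.5% | 6.3% |
| Plasma: Day 1, Weeks 12, 24, 52, 104, 156, 208, 260 | 8 | 1/9 = 11.1% | 5.6% |
| CSF, if data end at Week 52 | 3 | 1/4 = 25% | 12.5% |
| Plasma, if data end at Week 52 | 4 | 1/5 = 20% | 10% |

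With f = 1 the loss is zero in every row.

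**5. Illustrative power.** Assume complete data, compound symmetry with correlation ρ, a two-sided 0.05 test, and 80% power without the follow-up visit. With v(m) = (1 + (m − 1)ρ)/m and f = 0, power is Φ(2.802 × K/(K + 1) × √(v(K)/v(K + 1)) − 1.960). For K = 7 and ρ = 0.5 this is Φ(2.802 × 0.875 × 1.008 − 1.960) = Φ(0.511) = 69.5%. For ρ from 0.3 to 0.8, the full-schedule tau rows give about 69% to 74%, and the Week 52 rows about 56% to 64%. The extra visit adds too little precision to offset the dilution.

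**The case against.** The best counter-argument is that the follow-up was never meant to be a level of time. SAP 12.1 counts biomarker times from a first dose (in M15-563, or of ABBV-8E12), and Protocol 8.1.3 treats analysis time as length of time on drug. A visit scheduled from the last dose has no fixed place on either axis, so the scheduled times may mean only the week-numbered visits. This shows that the follow-up fits badly, but it does not exclude it. A programmer following SAP 5.1 literally would keep it.

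The direction of the effect is also not established. Falling drug level is not falling biomarker effect. Protocol 3.0 reports dose-proportional exposure, so a 2:1 exposure ratio could persist, and a log-scale contrast might persist with it. If the response saturates, the doses could even separate more at low concentrations. This stands: the dilution is conditional.

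The model also has a dose-by-time interaction, and SAP 12.1 describes each scheduled time, so a fading difference could be seen. That helps interpretation but leaves the tested composite unchanged.

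A reader might infer that including the sample contradicts the SAP 12.2 heading. The heading can be read simply as an analysis about at least a year of treatment, and the sentence under it is satisfied, so no contradiction is shown.

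**Conclusion.** The gap is real and worth closing. As written, SAP 5.1 and 12.2 together average a nearly drug-free sample, with no common study week, into the dose main-effect test for plasma and CSF tau.

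If the tau difference is fully lost by follow-up, the full-schedule contrast shrinks by about 8% to 12.5%. If half is lost, it shrinks by about 4% to 6%. These figures assume equal weights and a constant difference during the treatment period.

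Stronger readings are tempting but not supported:
- **The test is certainly diluted.** The documents give no tau effect and no time course after stopping. With no difference on drug, or one that persists, nothing is lost.
- **A loss of 20% to 25% is expected.** That requires data to end at Week 52, which the plan does not say.
- **MRI is affected in the same way.** The nominal weight would be 1/13 = 7.7% (12 times plus follow-up), but that assumes a difference in brain volume disappears within 20 weeks, which nothing supports.
- **This is the only test left in the SAP.** The imaging variables are tested too, and SAP 12.2 allows further analyses of other variables.

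The tau objectives are exploratory and the comparison is between two active doses, so the consequence is for interpreting the dose comparison, not for a primary claim.

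**What to change.** In SAP 5.1, limit the Longer-Term Biomarker Data Set to the M15-563 Day 1 pre-dose measurement and later measurements taken no more than 45 days after the subject's last M15-563 dose. State in SAP 12.1 that follow-up samples are summarised descriptively only.

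The 45-day window is already used for efficacy (Protocol 8.1.1) and safety (SAP 10.1). It keeps Week 260, because the last scheduled dose is at Week 256, 28 days earlier. Naming Day 1 and tying the window to M15-563 dosing keeps Day 1 samples from subjects who rolled over 46 to 56 days after their last M15-562 dose.

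The cost is one or two SAP sentences and a data filter, with slightly fewer samples in the model.

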5.5 Treatments

5.5.1 Treatments Administered

The solution contained in the study vial(s) of ABBV-8E12 must be diluted with 0.9% sodium chloride injection/solution for infusion. Subject weight will be obtained prior to study drug administration to determine the appropriate infusion rate as shown in the table below. Written instructions for the preparation of ABBV-8E12 solutions for infusion will be provided in a document that is separate from the protocol.

Subject's Weight in kg/lbs	Infusion Rate ^b
44 – 49 kg (97 – 109 lbs, inclusive) ^a	3.5 mL/min or 210 mL/hr
50 – 58 kg (110 – 128 lbs, inclusive)	4.0 mL/min or 240 mL/hr
59 kg and over (129 lbs and over)	4.7 mL/min or 282 mL/hr

- a. Subjects who weigh less than 44 kg (97 lbs.) will be excluded from enrollment (refer to exclusion criteria, Section 5.2.2, Exclusion Criterion 1).
- b. Continue infusion until bag is empty.

Study continuation for subjects whose weight falls below 44 kg (97 lbs.) during their participation will be discussed with the AbbVie TA MD and adjustment of the infusion rate or potential discontinuation from the study will be considered.

Study drug will be administered by IV infusion at each visit, in the morning if possible, as follows:

Study Drug	Formulation
ABBV-8E12 2000 mg	IV infusions at Day 1, Day 15, and Day 29, then every 28 days for up to 5 years
ABBV-8E12 4000 mg	
Placebo ^a	

- a. Subjects who received active drug in Study M15-562 will receive placebo on Day 15 to maintain the blind in Study M15-562; this is the only time point at which placebo will be dosed.

Note: Visits may be scheduled within ± 4 days.

Doses may be decreased after evaluation by the DMC of available safety, tolerability, and pharmacokinetic data.

The start and stop time of each study drug infusion will be recorded to the nearest minute.

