4.2 Study Design

This study is a long-term extension of the Phase 2, double-blind study, Study M15-562. Subjects who completed the 52-week Treatment Period in Study M15-562 will be eligible for enrollment into Study M15-563. All subjects in Study M15-563 will receive ABBV-8E12 as follows: 1) subjects who received placebo in Study M15-562 will be randomized, in a 1:1 ratio, to 1 of 2 ABBV-8E12 doses (2000 or 4000 mg); and 2) subjects who received ABBV-8E12 2000 or 4000 mg in Study M15-562 will continue on the same dose. Investigators and subjects will remain blinded to the treatment assignments in Study M15-562 after database lock and will be blinded to the dose level of ABBV-8E12 in Study M15-563.

Subjects who enroll in Study M15-563 from Study M15-562 will complete baseline procedures and receive their first infusion of study drug on Day 1 of Study M15-563. For subjects who do not have interruptions in study drug administration between Study M15-562 and Study M15-563, i.e., the duration between the last dose of study drug

[figure not shown]
infusion in Study M15-562 and the first dose of study drug in Study M15-563 is no more than 45 days, assessments that were performed at the Week 52 Visit in Study M15-562 will be used for the Day 1 Visit assessments in Study M15-563. If a subject enrolled in Study M15-563 is more than 45 days but less than 8 weeks since the subject's last dose of study drug in Study M15-562; in that case, Day 1 activities for Study M15-563 must be performed.

Subjects will receive 3 infusions of study drug during the first 4 weeks of Study M15-563, the first on Day 1, the second on Day 15 (subjects who received placebo in Study M15-562 will receive ABBV-8E12 on Day 15 of Study M15-563, and subjects who received ABBV-8E12 in Study M15-562 will receive placebo on Day 15 of Study M15-563 to maintain the blind in Study M15-562), and the third on Day 29. After Day 29, subjects will receive study drug infusions every 28 days and will continue to receive ABBV-8E12 until one of the discontinuation criteria is met, until the study is discontinued by the Sponsor, or until the study reaches completion. Subjects will return to the site approximately 20 weeks after their last dose for a post-treatment Follow-up Visit.

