4.3 Sample Size

The sample size for this study is dependent on the number of subjects who complete Study M15-562 and are qualified for enrollment into Study M15-563. A total of 330 subjects were planned for Study M15-562. Enrollment of M15-562 has been completed with totally 378 subjects randomized. The number of subjects who enroll in Study M15-563 could be up to 378.

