10.2.1 Adverse Event Overview

The number and percentage of subjects experiencing one or more adverse events in the following adverse event categories will be summarized for each treatment group and overall subjects in both Stand-Alone data set and the Cumulative data set. No comparisons of treatment groups will be performed.

- Any TEAE
- Any TEAE that was rated reasonable possibility of being related to study drug by the investigator
- Any severe TEAE
- Any serious TEAE
- Any TEAE that led to discontinuation of study drug
- Any fatal TEAE
- All deaths

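### No SAP safety summary combines subjects by current dose; dose-pooled columns and a stratified risk difference belong in the adverse event tables, and only there

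*SAP*

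**What the plan says.** SAP 6.0 gives the definition: "The data analysis will be conducted among treatment groups defined as Studies M15-562/M15-563", followed by the four sequences 2000/2000 mg, 4000/4000 mg, placebo/2000 mg and placebo/4000 mg. SAP 10 then reports safety by treatment group, with some variation:

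- Adverse event overview (10.2.1): counts "will be summarized for each treatment group and overall subjects in both Stand-Alone data set and the Cumulative data set".
- Adverse event incidence (10.2.2), laboratory shifts (10.3.2) and C-SSRS (10.6.1): each treatment group plus overall.
- Potentially clinically significant (PCS) laboratory, vital-sign and ECG values (10.3.3, 10.4.2, 10.5.2) and MRI safety (10.6.2): treatment group only, with no overall column stated.
- Mean changes (10.3.1, 10.4.1, 10.5.1): no columns named.

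No section defines a pooled 2000 mg or 4000 mg safety column. SAP 10.1 and 10.2.1 rule out comparisons of treatment groups, and Protocol 8.1.2.2 does the same for adverse event summaries.

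On how subjects come to a dose, SAP 4.2 says "subjects who received placebo in Study M15-562 will be randomized, in a 1:1 ratio, to 1 of 2 ABBV-8E12 doses"; subjects already on active drug keep their M15-562 dose. On size, SAP 4.3 says "Enrollment of M15-562 has been completed with totally 378 subjects randomized" and "The number of subjects who enroll in Study M15-563 could be up to 378". It gives no number per group and no expected roll-over.

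**The concern.** With no placebo arm left, the comparative safety question inside M15-563 is whether 4000 mg carries more harm than 2000 mg. The protocol treats dose as something that safety data may change: "Doses may be decreased after evaluation by the DMC of available safety, tolerability, and pharmacokinetic data" (Protocol 5.5.1), and Protocol 5.4.2 allows enrolment to a single dose group to be stopped. Protocol 5.6.4 predicts a smaller safety margin at 4000 mg (about 1.4-fold) than at 2000 mg (about 3-fold). For tau, SAP 12.2 does compare the two doses.

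For adverse events the reader gets the two doses each in two pieces, split by prior treatment, and where there is an overall column it mixes the doses. Each pair is less precise than both together, and no interval is given for either. A dose-related excess of moderate size could look unremarkable in each pair.

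**Working it through.** **Inputs.** At most 378 subjects (SAP 4.3). 1:1 randomisation of former placebo subjects (SAP 4.2). The current text does not state the parent allocation, so 1:1:1 is an assumption. Superseded text in the protocol's list of changes (220 active and 110 placebo of 330) agrees with one third on placebo, but the current text does not repeat that split for 378. The roll-over rate is not given; 100% is the ceiling and 70% is an illustrative lower value. The 10% incidence is also assumed.

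**The plan's own figure.** The documents give no power, margin or group size, so the only figure to check against is the ceiling of 378.

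- Early-start groups: 378/3 = 126 each.
- Placebo-start groups: 126/2 = 63 each.
- Sum: 126 + 126 + 63 + 63 = 378.
- Combined by current dose: 126 + 63 = 189 each.
- At 70% roll-over: 0.7 × 126 ≈ 88, 0.7 × 63 ≈ 44, 0.7 × 189 ≈ 132.

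**Precision of a dose difference.** Half-width = 1.96 × √(2 × 0.10 × 0.90 / n), with n per arm.

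| Contrast | n per arm, ceiling | SE (points) | 95% half-width (points) | n per arm, 70% | 95% half-width, 70% (points) |
|---|---|---|---|---|---|
| 2000/2000 vs 4000/4000 | 126 | 3.78 | 7.4 | 88 | 8.9 |
| placebo/2000 vs placebo/4000 | 63 | 5.35 | 10.5 | 44 | 12.5 |
| combined | 189 | 3.09 | 6.0 | 132 | 7.2 |

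The 70% half-widths are the ceiling values divided by √0.7.

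**Does stratifying cost precision?** Mantel-Haenszel weights are proportional to stratum size, here 2/3 and 1/3. The variance is (2/3)² × 0.18/126 + (1/3)² × 0.18/63 = 0.000635 + 0.000317 = 0.000952, so the SE is 3.09 points. That equals the unstratified SE at n = 189.

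**How far the gain depends on the assumptions.** Against the larger single pair, the variance falls by 1 − 126/189 = one third. If roll-over is equal across arms, this does not depend on its level. It does depend on the parent placebo share. At a 25% share the groups are about 142 and 47, and the fall is 25%. At a 50% share they are 94 and 94, and the fall is 50%. The combined ceiling stays at 189.

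**Rare events.** The chance that a dose shows no case of a 1% event is 0.99ⁿ: 28% at n = 126, 53% at n = 63 and 15% at n = 189.

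**The case against.** The case for leaving the tables alone has real content.

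- *The display follows the protocol.* The protocol synopsis and Protocol 8.0 prescribe the four sequences, and Protocol 8.1.2.2 plans no comparison of adverse events. This stands. The interval would be an addition and must be labelled as one.
- *Nothing is lost.* The sequences do not overlap, so counts by dose follow from adding two columns, and SAP 10.2.3 lists serious, fatal and discontinuation events. In the adverse event tables the overall column, with up to 378 subjects, would miss a 1% event only about 2% of the time (0.99^378). This is right for counts and for detecting an event at all. It does not supply a dose contrast or an interval.
- *Prior treatment matters.* Day 15 is active drug for placebo-start subjects and saline for the others, so first-exposure reactions may sit mainly in the placebo-start groups and be diluted by pooling. This is why the sequence columns must stay and the contrast must be stratified.
- *Pooling does not suit every table.* The Stand-Alone baseline is the last value before the first M15-563 dose. It is pre-drug for placebo-start subjects but comes after 52 weeks on drug for early-start subjects. A pooled mean change, or a pooled PCS count that requires a value more extreme than baseline, would mix two meanings of change. This stands, and it limits the fix to adverse events.

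A reader might also infer that the combined contrast is a clean randomised comparison. The documents do not support that. Within M15-563 only former placebo subjects are randomised to dose, and the sequence columns show that contrast intact. The early-start subjects were randomised in M15-562 but are now completers who qualified and rolled over, so dose-related dropout could have selected them.

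**Conclusion.** The gap is real: no SAP safety summary combines subjects by current dose. At the ceiling, combining the two pairs narrows the 95% half-width at 10% incidence from 7.4 points (the larger pair) to 6.0. The figures 126, 63 and 189 are upper limits that rest on 1:1:1 parent allocation and full roll-over. The gain is moderate and the cost small, so the change should be made, but nothing planned is invalid without it.

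Three wider readings go too far:

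- That dose is ignored throughout. The protocol synopsis tabulates anti-drug antibody titers by dose level. Pharmacokinetics offers no contrast with safety, since Protocol 8.1.4 and SAP 11.0 also break serum concentrations down by prior treatment.
- That every safety table has the four sequences plus an overall column. PCS and MRI summaries state no overall column, and the mean-change sections name no columns.
- That the DMC must work from these columns. SAP 4.4 leaves the detail to a charter that is not among the documents, and Protocol 5.5.5 gives the DMC full access to data as needed for safety assessment.

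**What to change.** In SAP 10.2.1 and 10.2.2, for the Stand-Alone data set:

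1. Keep the four sequence columns and add 'All 2000 mg' (2000/2000 plus placebo/2000) and 'All 4000 mg' (4000/4000 plus placebo/4000).
2. For the overview rows on any, severe, serious, related and discontinuation TEAEs, add a descriptive 4000-minus-2000 risk difference with 95% CI, stratified by prior treatment (Mantel-Haenszel).
3. Amend the no-comparison statements in SAP 10.1 and 10.2.1 to allow this interval, say that it is descriptive, and note that Protocol 8.1.2.2 did not plan it.
4. State beside the result that the early-start stratum is limited to M15-562 completers who rolled over.
5. Do not add the pooled columns to the mean-change tables or to PCS tables defined relative to baseline.

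The cost is slightly wider tables and one unplanned interval for each of these overview rows. No new data are needed.
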